## **2 STUDY OBJECTIVES**

The aims of this proposal are to conduct a clinical study of a small group of patients with SSADH deficiency before and during a therapeutic trial of SGS-742, assessing the effect on cortical excitability and neuropsychological function. We hope to establish validated markers in SSADH-deficient patients that can be measured during therapeutic intervention. Data acquired in this study should have relevance to conditions beyond SSADH deficiency, as they will enhance our ability to understand inborn metabolic errors that present with prevalent phenotypes such as intellectual disability or autism spectrum disorder, and to make optimal therapeutic decisions in SSADH deficiency patients.

### **2.1 Hypotheses:**

H1: Patients will show improvement in the Auditory Comprehension subtest of the Neuropsychological Assessment Battery Language Module during treatment with SGS-742 and improvements in activities of daily living based on parent questionnaire.

H2: Patients with SSADH deficiency will have lengthening toward normal values of the cortical silent period, and return of long interval intracortical inhibition, during a therapeutic trial of SGS-742

H3: Patients will show improvement on global assessment ratings

### **3. SUBJECT POPULATION**

#### **3.1 Description of Study Population**

The proposed research protocol will investigate patients with documented succinic semialdehyde dehydrogenase deficiency, a rare autosomal-recessively inherited defect of 4-aminobutyric acid (GABA) metabolism. We propose to enroll 22 patients with SSADH deficiency with the goal of obtaining 16 completers for the cross-over study. Those who withdraw before completion of at least 3 months of their second treatment phase will be replaced.

#### **3.2 Inclusion Criteria (See checklist Appendix 1)**

- 4-hydroxybutyric aciduria (gamma-hydroxybutyric aciduria) on two separate tests.
- Documented succinic semialdehyde dehydrogenase enzyme deficiency.
- Patients must have clinical features consistent with SSADH deficiency including developmental delay especially deficit in expressive language, hypotonia, ataxia, seizures, and other neuropsychiatric symptoms including sleep disturbances (45%), attention deficit (45%), anxiety (27%), obsessive-compulsive disorder (25%), and autistic traits (25%).
- During the study, women of child-bearing potential must use a reliable method of birth control until one month after the final drug taper is complete.
- Patients will be 4 years or older.
- Based on HSPU/ACAT evaluation must meet one of the following criteria:
  - subject has capacity to consent
  - subject has a documented legal guardian to provide consent
  - subject lacks capacity and no legal guardian but HSPU determines 1) the subject has a DPA, or 2) the subject has capacity to designate an NIH DPA, or 3) a Next of Kin surrogate may be appointed as outlined in MAS 87-4.

#### **3.3 Exclusion Criteria (See checklist Appendix 1)**

- Current alcohol use (>14 drinks/wk in men and >7 drinks/wk in women) or recreational drug use for the 16 month period of this study.
- Patients with a history of other major medical disorders with clinical fluctuations, or requiring therapy that might affect study participation or drug response such as severe depression or psychoses, renal or hepatic disease.

- Patients requiring treatment with drugs known to affect the GABAergic system, including vigabatrin and benzodiazepines.
- Pregnant and lactating women

#### 4. STUDY DESIGN AND METHODS:

##### 4.1 Study overview

This is a 16-21 month randomized, double-blind cross-over phase two clinical trial of SGS-742 versus placebo in 22 patients age 4 years and older with SSADH deficiency.

##### 4.1.1 Study Phases (see Study Schedule Appendix 2):

- Screening (1-3 days)—outpatient. May be combined with baseline visit.
- Baseline visit (1 - 3 days)—inpatient or outpatient. The first dose of study pills will be administered at the NIH. The patient will stay for 30 – 90 minutes following the first dose. The patient will be permitted to return to local accommodations overnight and return 12 - 24 hours after the first dose to be assessed for any skin reactions, and then discharged home.
- Titration one: 9 - 15 days (titration is 9 days and if they only get one or two doses on day one they will have an additional day of drug titration).

Phase 1 (six months +/- 2 weeks of SGS-742 or placebo)—during phase one there will be regular communication, at least once every two weeks, with patients/families by phone and/or the clinical trial database. If indicated, based on reports during these regular communications, an outpatient visit will be arranged at NIH or with a local provider for safety monitoring or pregnancy testing. If this is to be done by local providers, we will have patients designate the local provider in advance. We will contact the local provider and arrange for payment of any visits or testing by the NIH and also document a plan in the progress notes for how individual providers will communicate findings and test results. We will request local providers provide written documentation of outpatient visits and pregnancy testing results by facsimile to include in the NIH patient medical record.

- End of phase 1 testing: (At 6 mo +/-2 weeks of phase 1) inpatient or outpatient 3 day evaluation including: EEG, TMS, neuropsychological tests, blood and urine tests, and optional LP, MRI/MRS.
- Washout 9 weeks (+/- 2 weeks), including 9 days to taper and discontinue phase I medication, at least 7 weeks medication free and titration to phase 2 medication 9 - 15 days (**taper is 9 - 15 days and if they only get one or two doses on day one they will have an additional day of drug taper**).

Phase 2 (six months +/- 2 weeks of phase 2 treatment)— during phase two there will be regular communication, at least once every two weeks, with patients/families by phone and/or the clinical trial database. If indicated, based on reports during these regular communications, an outpatient visit will be arranged at NIH or with a local provider for safety monitoring or pregnancy testing. If this is to be done by local providers, we will have patients designate the local provider in advance. We will contact the local provider and arrange for payment of any visits or testing by the NIH and also document a plan in the progress notes for how individual providers will communicate findings and test results. We will request local providers provide written documentation of outpatient visits and pregnancy testing results by facsimile to include in the NIH patient medical record.

- End of phase 2 testing: (At 6 mo +/-2 weeks of phase 2) inpatient or outpatient evaluation including: EEG, TMS, neuropsychological tests, blood and urine tests, and optional LP, MRI/MRS.
- Taper off drug: 9 – 15 days.
- Final visit: 4-7 weeks after completion of the final drug taper.

Some variability in scheduling will be based on whether a participant has a seizure.

## **4.2 Recruitment**

Most subjects will be patients with SSADH deficiency followed by [name] in the Boston Children's Hospital Neurology Department. [name] may be the treating clinician for these patients or patients may be referred to him by their treating physicians specifically for consultation regarding management and treatment of SSADH deficiency. During the course of routine clinical care, patients will be informed about the study and, upon their request, will be provided the information to contact the NIH personnel on their own initiative. The referral will not be made directly by [name] and the NIH is not contacted by [name] on behalf of the patient.

Letters will also be mailed to families with a history of SSADH and the letter will be posted to the SSADH Association website (See Appendix VII).

## **4.3 Screening**

Consent will be obtained before any study procedures, including screening procedures, are done.

Patients will be screened in the CES outpatient clinic for inclusion in the protocol by CES physicians or licensed practitioners. [name], who is a special volunteer at NIH with clinical privileges, will supervise confirmation of the diagnosis. Screening will include review of the information collected by the referring doctors to determine suitability for the protocol, physical and neurological examination, urine tests to confirm the diagnosis if not performed previously, electrocardiogram, CBC, blood chemistries, and antiepileptic drug levels if clinically indicated and the testing is available in our lab.

#### **4.4 Study Procedures**

All procedures performed at NIH will be for research. Each procedure will be performed at baseline and at the end of each 6-month treatment arm (3 total). Procedures include electroencephalogram, neuropsychological testing, transcranial magnetic stimulation, and optional lumbar puncture and optional MRI/MRS. All participants will be asked to undergo LP, however, refusal to have an LP or inability to tolerate an LP will not be exclusionary for the study.

TMS and optional MRS will not be done within 24 hours of a reported seizure. The studies will be rescheduled.

At each visit during drug treatment, patients will have a medical history and physical examination and will review seizure calendars and be asked about adverse effects. Laboratory tests, including urine pregnancy for females of child bearing potential, will be obtained if indicated based on a change in clinical status.

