#### 4.4.9: Pregnancy tests

Patients of child-bearing potential will have a urine pregnancy test at screening and each out-patient visit. Pregnancy testing may also be done based on safety monitoring and clinical assessment. Pregnancy testing may be done by local providers. In this case, we will have patients designate the local provider in advance. We will contact the local provider and arrange for payment of testing by the NIH and also document a plan in the progress notes for how individual providers will communicate test results. We will request local providers provide written documentation of pregnancy testing results by facsimile to include in the NIH patient medical record.

As outlined in the minor assents, if the pregnancy testing for a minor patient, performed at the NIH or through a local provider, is positive, we will inform the parent or guardian.

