### **4.5 Drug Treatment**

#### 4.5.1 Randomization

A crossover design will be employed where patients are randomized into a six-month trial of treatment versus placebo.

Subjects will be randomized at the end of baseline testing to either active drug or placebo using a 1:1 ratio per the randomization schedule. The randomization schedule will be generated, secured, distributed, and stored by the NIH Pharmacy.

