#### 4.5.2 Study Drug Administration

Patients may be outpatients or inpatients during titration. The first dose of study pills will be administered at the NIH. The patient will stay for 30 – 90 minutes following the first dose. The patient will be permitted to return to local accommodations overnight and return 12 - 24 hours after the first dose to be assessed for any skin reactions, and then discharged home.

All patients will be given an exact written titration schedule to follow, and will be contacted by phone and/or clinical trials database at least every two weeks during the study.

Following a 9 week +/- 2 weeks total washout period, including drug taper, described below, patients will enter the other treatment arm. For the second phase of the study patients may also be inpatients or outpatients. The first dose of study pills will be administered at the NIH. The patient will stay for 30 – 90 minutes following the first dose. The patient will be permitted to return to local accommodations overnight and return 12 – 24 hours after the first dose to be assessed for any skin reactions, and then discharged home.

The active treatment will be SGS-742, synthesized by IRIX pharmaceuticals in a GCP facility. The target dose will be 10 mg/kg with a maximum of 600 mg given orally three times daily for six months, with an increasing titration over nine to fifteen days. The placebo arm will be inert placebo given orally three times daily. It is recommended to take the medication three times each day prior to meals because administration of food decreases oral systemic availability of SGS-742. The drug and matching placebo will be encapsulated by the NIH pharmacy. The pharmacy will draw up a randomization schedule and ensure blinding.

Patients and examining physicians will be blinded as to the treatment arm in which the patient is enrolled.

The NIH Pharmacy will dispense three month's supply of study drug (SGS-742 or placebo) to subjects for each study treatment phase. The second three-month supply can be picked up by the patient or sent by mail. Patients will be asked to bring study pill bottles to each clinic visit. Pill counts will be performed at each visit if patients bring study pill bottles. Patients will be advised to take a missed dose if they remember within 4 hours; otherwise, to take the next scheduled dose and record the missed dose on their seizure/medication calendar. Patients will be advised to take their study drug about one hour before food.

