## 7. RISKS AND DISCOMFORTS

### 7.1 SGS-742

Patients are at risk for developing an allergic reaction to the study pills.

Animal toxicology studies showed development of ataxia at doses of 100-300 mg/kg in mice and rats, and seizures at > 300 mg/kg. In 6/12-month oral toxicity studies, the clear "no observable effect" level in dogs was 100 mg/kg; in rats, the only observation was a slight reduction in body weight gain in males at 200 and 600 mg/kg. Gastrointestinal and hepatic toxicity was found after administration of 300 mg/kg for three months in rats.

In the phase 2 blinded placebo-controlled study, the following side effects occurred in more than 5% of subjects:

	Active drug (n=75)	Placebo (n=35)
Diarrhea	8%	8%
Nausea	8%	6%
Dizziness	7%	3%

Side effects reported less frequently included headache, arthralgia, peripheral edema, unspecified infections, infestations, respiratory, and skin disorders. These did not differ between subjects taking active drug and placebo.

Three serious adverse events were reported. One syncopal episode occurred in a patient with a previous history of transient ischemic attacks lasted 30 minutes, resolving spontaneously without medical intervention or sequelae. One

intraocular hemorrhage occurred in a patient on warfarin. One subject had a preexisting liver function test elevation that did not change on SGS-742.

There were no clinically significant changes in laboratory tests, vital signs, weight, or ECG results.

SGS-742 is not metabolized, and >99% of the drug is excreted unchanged in urine. Thus, no clinically important drug interactions are anticipated.

Pregnancy testing and contraception:

Since the teratogenic potential of SGS-742 is unknown, women of child-bearing potential must use an effective form of birth control during the study and for a month after final drug taper is complete. Patients should not breast-feed during the study or for one month after the study is completed.

Effective methods of contraception for this study include

1. hormonal contraception (birth control pills, injected hormones or vaginal ring);
2. intrauterine device;
3. barrier methods (condom or diaphragm) combined with spermicide;
4. surgical sterilization (hysterectomy, tubal ligation, or vasectomy in a partner).

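### The protocol does not require a negative pregnancy test before the first Phase 2 dose, and its routine testing rule does not reach an in-patient start

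*Combined protocol and SAP*

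**What the plan says.** Two sections of the protocol set the timing of pregnancy tests.

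- Section 4.4.9 gives the routine rule: "Patients of child-bearing potential will have a urine pregnancy test at screening and each out-patient visit". It then allows further tests prompted by safety monitoring or clinical assessment.
- Section 4.4, on visits during drug treatment, is conditional: "Laboratory tests, including urine pregnancy for females of child bearing potential, will be obtained if indicated based on a change in clinical status".

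The start of Phase 2 is described in Section 4.5.2. It is timed as "Following a 9 week +/- 2 weeks total washout period, including drug taper", and on setting the section says "For the second phase of the study patients may also be inpatients or outpatients". The first dose is given at NIH, followed by a short stay and a skin check the next day. No pregnancy test is mentioned. Section 4.1.1 breaks the washout into parts, "including 9 days to taper and discontinue phase I medication, at least 7 weeks medication free", and lists the titration to the second treatment with them.

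At entry, Section 3.3 excludes "Pregnant and lactating women". Sections 7.1 and 8 stop the study drug if a participant proves to be pregnant.

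**The concern.** Section 7.1 justifies contraception with the words "Since the teratogenic potential of SGS-742 is unknown". A rule that stops the drug on a positive test protects a participant only if a test is done, and protects fully only if the result is known before dosing.

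The Phase 2 start is the weak point. Section 4.5.1 states: "Subjects will be randomized at the end of baseline testing to either active drug or placebo using a 1:1 ratio". About half of the patients (11 of 22 if enrolment is complete and evenly split) therefore take placebo first, and their first Phase 2 dose is their first exposure to SGS-742. Phase 1 is largely covered by the screening test and the pregnancy exclusion. Nothing equivalent is stated for the crossover, which comes after a washout of many weeks. At stake is participant and fetal safety, not the treatment comparison.

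**Working it through.** The plan gives no figure to reproduce. The check is a reading of each place where a pre-dose rule could stand, followed by one timing calculation.

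**Where a rule could stand**

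- Section 3.3 excludes pregnancy at entry and states no re-check at crossover.
- Section 4.1.1 arranges interim visits for pregnancy testing only when the regular contacts suggest a need.
- Section 4.4 makes testing at on-treatment visits conditional on clinical change. The Phase 2 start follows a drug-free interval, so it is arguably not an on-treatment visit at all.
- Section 4.4.9 makes testing routine at screening and out-patient visits. It does not mention in-patient stays or link the result to dosing.
- Section 4.5.2 sets out the first Phase 2 dose in some detail and names no pregnancy test.
- The Section 4.8 schedule marks urine tests at screening and at Month 6 of each phase, without naming pregnancy. The second titration row has no mark for a clinic visit or a urine test.
- Section 7.2 requires a test before MRI/MRS, but the scan is optional and under that section a positive result cancels only the scan.
- Section 11.5 lists pregnancy testing as a protection, without timing.

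None of these requires a negative result before the first Phase 2 dose.

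**By setting of the Phase 2 start**

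- Out-patient: Section 4.4.9 requires a test at the visit, and Sections 7.1 and 8 stop the drug on a positive result. Only the order of test and dose is unstated.
- In-patient: no section expressly requires a test.

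**Age of an end-of-Phase-1 test at the first Phase 2 dose**

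This assumes that a pregnancy test is among the Month 6 urine tests and is done as the taper begins.

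- By Section 4.5.2: 9 ± 2 weeks = 7 to 11 weeks; 63 ± 14 = 49 to 77 days.
- By the parts in Section 4.1.1: 9 days of taper + 7 × 7 = 49 drug-free days gives 9 + 49 = 58 days at least (58 / 7 = 8.3 weeks).
- If the second titration (at least 9 days) is counted inside the 77-day limit, as Section 4.1.1 lists it, the latest first dose is day 77 − 9 = 68.

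The 7-week end of the first range cannot be reached if the stated taper and drug-free minimum are both kept. On either account, a test at the end of Phase 1 does not show pregnancy status on the day of the first Phase 2 dose.

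**The case against.** The strongest reply is that the protocol already covers most of this. Section 4.4.9 is the dedicated section and its rule is mandatory; Section 4.4 can be read as the prompted layer on top of it, so the difference between them may be only wording. The Phase 2 start reads mainly as an out-patient workflow, since patients may stay in local accommodation overnight, and such a start triggers a test. Dosing after a known positive result would contradict Sections 7.1 and 8. Contraception is mandatory until one month after the final taper (Sections 3.2 and 7.1), so it spans the washout. Contact is at least every two weeks in both treatment phases (Section 4.1.1). Section 1.4 reports adverse maternal and fetal effects in rats at 2000 mg/kg and none at 600 mg/kg. The study calendar, eligibility checklist and case report forms listed in Section 25 are not in the public document and could hold a pre-dose check.

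Most of this stands, and it limits the point to a minor one. It does not supply a rule for an in-patient start or put the result before the dose. The rat data do not settle human risk, which the protocol itself calls unknown.

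A reader might go further and infer that a patient's last test could be the one at screening, more than half a year before the Phase 2 dose. The documents do not establish that. It would need in-patient stays at both the end of Phase 1 and the Phase 2 start, no MRI/MRS, and Month 6 urine tests that leave out pregnancy. Sections 4.1.1 and 4.8 schedule those urine tests unconditionally and do not say what they contain. Nor do the documents support the inference that Phase 2 patients in general would be dosed untested.

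**Conclusion.** The point holds in a limited form. The public protocol does not require a negative pregnancy test before the first Phase 2 dose. For out-patient starts, what is missing is the order of result and dose. For in-patient starts, the test requirement itself is missing. A test from the end of Phase 1 would be about 7 to 11 weeks old, or at least 58 days by the parts of the washout.

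This rests on the text of the public document; a rule in the appendices would reduce the point to carrying that rule into the body text. Neither the number of participants of child-bearing potential nor the frequency of in-patient starts is given, so the number of participants affected cannot be estimated. It is a minor safety improvement, and the efficacy analysis is unaffected.

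**What to change.** Amend Section 4.4.9 to require a negative urine pregnancy test before the first dose of each phase, whether the patient is an in-patient or an out-patient. Align Section 4.4 with it, keeping clinically prompted tests as an addition. Mark the test in the Section 4.8 schedule at the start of each phase. A screening test combined with the baseline visit can serve for Phase 1.

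The cost is one or two sentences, schedule marks and a few extra urine tests. No new visit is needed, because the first dose of each phase is already given at NIH.

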##### **4.4.1 Structural MRI Scans (OPTIONAL)**

3.0 Tesla anatomical T1 and T2-weighted MRI images will be obtained both for clinical evaluation and partial volume correction / co-registration for MRS. Approximately 45 minutes will be needed to obtain the images.

##### **4.4.2 Magnetic Resonance Spectroscopy (MRS) (OPTIONAL)**

MRS will be performed using a 3-T whole-body scanner and a transmit-receive head coil. MRS spectra will be acquired from 2 voxels globus pallidus and cerebral cortex (frontal or parietal). GABA will be measured using an interleaved PRESS-based J editing method (Hasler et al 2005). The study will last a maximum of 90 minutes.

